### 3 STUDY DESIGN

#### 3.1 Main study design

This study is a prospective, randomized, blinded clinical trial to assess the safety of simultaneous RZV and alIV4 versus simultaneous RZV and HD-IIV4 in 400 adults age  $\geq 65$  years. Older adults who have not received IIV during the 2021-2022 and 2022-2023 influenza seasons will be enrolled. Detailed health and demographic data will be collected from study participants at baseline prior to influenza vaccine receipt. With Day 1 serving as the day of vaccination, participants will be followed through Day 8 (total 8 days) for symptoms of reactogenicity as described in **Section 5.4**. Vaccinations will be performed by unblinded study staff with all follow-up assessments being conducted by blinded staff. Study subjects will be blinded throughout the study. Participants will be followed through Day 43 after each dose of RZV for adverse events and adverse events of clinical interest, including health care utilization, and through the entire period of enrollment for serious adverse events and immune-mediated diseases, as described in **Section 5.4 and 5.5**.

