**Table 1. Proposed Schedule of Events**

Study Visit	Visit 1	Visit 2	Visit 3	Visit 4	Visit 5	Visit 6	Visit 7	*Visit 8 (a)	Visit 9
Study Day	1	3	9	29	43	60	69	90	103
Visit Window (Days)	n/a	3-6	9-16	29-34	43-50	60-65	69-76	90-97	103-110
Type of contact	Clinic	Reminder (e-mail, Text or phone call)	Phone	Clinic	Phone	Clinic	Phone	Clinic	Phone
Obtain serious adverse event information and Adverse events of clinical interest			X	X	X	X	X	X	X
Obtain health care utilization data			X	X	X				

a. \*Visit 8 will occur at JHU site only

b. Blood draws on Visit 6 (Day 60) and Visit 8 (Day 90) will occur at JHU site only for future use

c. Symptom diary (solicited local and systemic reactogenicity events) and EQ-5D to be completed by participant on Days 1-8 after vaccination, and days 60-68 after second dose of RZV

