### **5.4 Reactogenicity and Safety Assessment**

Participants will be assessed for any immediate reactogenicity in a period at least 15 minutes after vaccine administration while at the study site. They will be assessed for the following potential systemic reactions such as anaphylaxis related symptoms (e.g., dyspnea, chest tightness, wheezing, cough, stridor, urticarial, flushing, nasal congestion, dizziness, syncope, diaphoresis, emesis) or other medical symptoms (e.g., feverishness (chills/shivering/sweating), fatigue, malaise, myalgia, arthralgia, headache, and gastrointestinal symptoms (nausea, vomiting, diarrhea, abdominal pain). They will be assessed for any potential injection site reactions including pain, erythema or induration. Pain severity will be assessed on a 0 – 10 scale with 10 being the worst pain imaginable and 0 being no pain.

Frequency and occurrence of solicited local and systemic reactogenicity will be assessed daily through post- vaccination Day 8 using a standard memory aid. Unsolicited adverse events (AEs) will be assessed daily through post-vaccination Day 42 following each vaccination visit. Serious AEs (SAEs) and adverse events of clinical interest including new onset of immune-mediated diseases and concomitant medication use will be assessed daily through the entire period of a subject's participation.

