#### 5.4.3 Reporting of Adverse Events

An adverse event (AE) is any untoward medical occurrence in a patient or clinical investigation subject administered a pharmaceutical product and which does not necessarily have to have a causal relationship with this treatment.

If indicated, AEs occurring during the study will be reported to the Vaccine Adverse Event Reporting System (VAERS). The National Childhood Vaccine Injury Act requires healthcare providers to report the following AEs to VAERS:

- Any adverse event listed by the vaccine manufacturer as a contraindication to further doses of the vaccine; or
- Any adverse event listed in the [VAERS Table of Reportable Events Following Vaccination \[PDF - 75KB\]](#) that occurs within the specified time period after vaccination.

In addition, CDC encourages reporting of any clinically significant adverse event that occurs in a patient following a vaccination, even if there is uncertainty regarding if a vaccine caused the event.

SAE and AE reporting will occur consistent with institutional policy. The original verbatim terms used by investigators to identify SAEs and adverse events of clinical interest in the case report form will be mapped to preferred terms using the Medical Dictionary for Regulatory Activities (MedDRA) dictionary (<http://www.meddra.org/>).

Vaccine-related SAEs will be medically attended per routine care.

SAEs will be reported promptly to the overseeing IRBs in accordance with institutional procedures. Any unanticipated problems resulting from study conduct related to participation will be reported promptly to the reviewing IRBs and CDC, in accordance with institutional procedures.

The period for monitoring and reporting SAEs will occur for the duration of study participation (42-days post vaccination)

The study will report only SAEs occurring during each subject's participation in the study.

More information on potential risks and benefits is located under Human Subjects, **Section 8.3**.

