## **5.5 Health Care Utilization**

Participants will be asked to report health care utilization including: telephone calls to the medical provider for medical advice, e-mail portal, electronic health record, clinic visits, urgent care visits, emergency department visits and hospital admissions occurring through day 43 according to the schedule in Error! Reference source not found. above. The reason for health care use will also be obtained. Electronic or paper health records will be obtained and reviewed to confirm reports of clinic visits, urgent care visits, emergency department visits and hospital admissions. Health care utilization and the reason for health care utilization will be recorded on the symptom diary.

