## **8.3 Potential Risks and Benefits**

RZV, allV4, and IIV-HD4 are FDA-licensed vaccines approved for use in adults  $\geq 65$  years old. These vaccines are standard clinical practice and recommended by the CDC. Participants will be provided with the CDC Vaccine Information Statement (VIS) for IIV and RZV (<https://www.cdc.gov/vaccines/hcp/vis/vis-statements/flu.pdf> and <https://www.cdc.gov/vaccines/hcp/vis/vis-statements/shingles-recombinant.pdf>).

Syncpe (fainting) can occur in association with administration of injectable vaccines. Sitting or lying down for about 15 minutes can help prevent fainting, and injuries caused by a fall, as recommended in the ACIP General Recommendations on Immunization(30). Subjects should inform their doctor should they feel dizzy, or have vision changes or ringing in the ears.

IIV risks include minor problems such as soreness, redness, swelling, or pain where the shot was given, hoarseness, sore, red or itchy eyes, cough, fever, aches, headache, itching, fatigue, all of which usually occur within 1-2 days of vaccination and are self-limiting. Some people get severe pain in the shoulder and have difficulty moving the arm where a shot was given. This happens very rarely. More serious problems including a small increased risk of Guillain-Barré Syndrome estimated at 1 or 2 additional cases per million people vaccinated. This is much lower than the risk of severe complications from influenza infection, which can be prevented by IIV(31). In addition, any medication can cause a severe allergic reaction, or anaphylaxis, which is estimated at  $\sim 1$  in one million doses of IIV administered (32).

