4 STUDY DESIGN

4.1 Main Study Description

This study is a prospective, randomized, blinded clinical trial to assess the safety of simultaneous RZV and allIV4 versus simultaneous RZV and HD-IIV4 in 400 adults age ≥ 65 years. Older adults who have not received RZV (Shingrix vaccine) or IIV during the 2021-2022 and 2022-2023 influenza seasons will be enrolled; participants enrolling in the 2022-2023 influenza season may have received influenza vaccine in the prior season. Detailed health and demographic data will be collected from study participants at baseline prior to influenza vaccine receipt. With Day 1 serving as the day of vaccination, participants will be followed through Day 8 (total 8 days) for symptoms of reactogenicity. Vaccinations will be performed by unblinded study staff with all follow-up assessments being conducted by blinded staff. Study subjects will be blinded throughout the study. Participants will be followed through Day 43 after each dose of RZV for adverse events and adverse events of clinical interest, including

health care utilization, and through the entire period of enrollment for serious adverse events and immune-mediated conditions (see Appendix A).

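### Health care utilization is promised after each RZV dose but scheduled only after dose 1, and non-serious unsolicited or medically attended events have no between-arm analysis

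*Protocol*

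**What the plan says.** **Utilization, as promised.** Protocol 3.1 has participants followed through Day 43 "after each dose of RZV for adverse events and adverse events of clinical interest, including health care utilization". SAP 4.1 repeats it: "Participants will be followed through Day 43 after each dose of RZV for adverse events and adverse events of clinical interest, including", and the sentence continues with health care utilization.

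**Utilization, as scheduled.** In the Protocol's Proposed Schedule of Events, the row "Obtain health care utilization data" is marked at Visits 3, 4 and 5 only. Protocol 5.5 lists the contacts to be reported, ending with "hospital admissions occurring through day 43". The Unscheduled Visits text in Protocol 5.1 also stops utilization at day 43. The descriptions of Visits 6 to 9 do not mention it. Protocol 5.5 adds that utilization is written on the symptom diary.

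**Unsolicited events.** Protocol 5.4: "Unsolicited adverse events (AEs) will be assessed daily through post-vaccination Day 42 following each vaccination visit". The same section grades them 1 to 3, and Protocol 5.4.2 has investigators judge relatedness. Protocol 5.4.3 limits dictionary coding to verbatim terms used to "identify SAEs and adverse events of clinical interest in the case report form will be mapped to preferred terms".

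**Analysis.** Secondary Objective 3 (dose 1) and Exploratory Objective 4 (dose 2) cover serious adverse events and adverse events of clinical interest. No objective, outcome measure or analysis in either document covers other unsolicited events or utilization. Protocol 5.4 does provide for periodic review of new medical conditions by a safety-monitoring panel.

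**The concern.** Two things do not fit together. First, a stated follow-up property, utilization after each dose, is not delivered by the schedule that sites will work from. The effect goes beyond utilization, because under Protocol 5.5 a reported visit is what leads staff to obtain and check clinic, urgent care and emergency records. After dose 2 that prompt is missing.

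Second, the trial exists because no safety data are available for this vaccine combination (Protocol 1.2 and 5.4.4). It collects, grades and attributes unsolicited events after both doses, but plans no comparison of them. Take a Grade 3, related, unsolicited event that is seen in an emergency department without admission. If it is neither judged serious nor an event of clinical interest, it enters no arm comparison. A difference between arms in such events could go unreported even though the data were in hand.

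**Working it through.** **Step 1: the windows side by side.** Day 1 is the day of dose 1; dose 2 is planned for Day 60 (window 60–65).

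| Item | Stated | Scheduled after dose 1 | Scheduled after dose 2 |
|---|---|---|---|
| Utilization | Through Day 43 after each dose (Protocol 3.1, SAP 4.1) | Visits 3, 4, 5 (Days 9, 29, 43) = 3 contacts | 0 contacts |
| Unsolicited events | Through Day 42 after each vaccination (Protocol 5.4) | Visits 3, 4, 5 = 3 contacts | Visits 7, 8, 9 (Days 69, 90, 103) = 3 contacts, Visit 8 at the Johns Hopkins site only |

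The Day 43 cut-off falls 60 − 43 = 17 days before planned dose 2, so no reading of study Day 43 reaches it.

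**Step 2: can the diary fill the gap?** A diary is issued again at Visit 6, and Protocol 5.5 says utilization is recorded on the diary. Protocol 8.2 gives the diary's medical-intervention item for study days 1–8. The second diary runs over Days 60–68. At best it covers about the first week after dose 2, not 42 days, and the documents do not say that it carries the item.

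**Step 3: would existing calls cover the window?** If dose 2 is on Day 60, Visit 9 on Day 103 is 103 − 60 = 43 days later. If dose 2 is on Day 65, 42 days later is Day 107, inside the Visit 9 window (103–110). No new visit is needed.

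**Step 4: count of planned between-arm analyses.**
- Solicited reactions, which need not be serious: 8 (the Primary Objective, Secondary 1 and 2, Exploratory 1, 2, 3, 5 and 6).
- Serious events and events of clinical interest: Secondary 3 and Exploratory 4. Events of clinical interest need not be serious.
- Quality of life: Exploratory 8.
- Other unsolicited events: 0.
- Utilization: 0.

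**Step 5: would a table be informative at the planned size?** The plan's own size is reproduced first, with a 14% rate in both arms, margin 0.10, one-sided alpha 0.025 and power 80%:

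n per arm = (1.960 + 0.842)² × 2 × 0.14 × 0.86 / 0.10² = 7.849 × 0.2408 / 0.01 ≈ 189.001, rounded up to 190. Total 380; 380 / 0.95 = 400. This matches the plan.

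Neither document gives a rate for unsolicited events or utilization, so a range is assumed, equal in both arms. The Wald 95% half-width for the arm difference is 1.96 × √(2p(1 − p)/n):

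| Assumed p | n = 190 per arm | n = 200 per arm |
|---|---|---|
| 5% | 4.4 points | 4.3 |
| 10% | 6.0 | 5.9 |
| 20% | 8.0 | 7.8 |
| 30% | 9.2 | 9.0 |
| 40% | 9.9 | 9.6 |

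For example, at 10% with n = 190: 1.96 × √(0.18/190) = 1.96 × 0.0308 = 0.060. The table would be descriptive, but precise enough to be worth reporting.

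**The case against.** A reader might infer that non-serious harm as a whole is lost from this safety trial. The documents do not support that. The primary endpoint is itself a comparison of reactions that need not be serious, seven further analyses follow it, and new immune-mediated disease is compared whether serious or not. A Grade 3 solicited reaction within the diary window that leads to an emergency visit counts in the primary endpoint at dose 1 and in Exploratory Objective 1 at dose 2. The seriousness definition also admits important medical events without hospitalization.

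A reader might also take the risk in Protocol 8.3, "Some people get severe pain in the shoulder and have difficulty moving the arm where a shot was given", as visible only in the unanalysed data. That goes too far. Injection-site pain on moving the limb or at rest, arthralgia and myalgia are all solicited and graded, so such pain on days 1–8 can enter the analysed endpoints. Only later onset would be missed. The hoarseness and eye symptoms in Protocol 8.3 are not in the solicited tables, but the protocol presents them as minor and self-limiting.

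Nor is half of all follow-up after dose 2 missing. Serious events and events of clinical interest are asked about at Visits 6 to 9 (Visit 8 at one site), and records are reviewed for serious events and new immune-mediated disease throughout.

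It can fairly be added that both arms receive RZV alone at dose 2, that every dose 2 objective is exploratory, and that unsolicited events do have a stated use in safety-panel review and reporting. The safety monitoring plan (Appendix G) is not in the available text, so by-arm tabulation there cannot be excluded. These points lower the stakes. They do not remove the contradiction on utilization, and monitoring during the trial is not an analysis in its results.

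Protocol 7.1.4 speaks of severe adverse events for Secondary Objective 3 and Exploratory Objective 4. Read literally, that could bring in Grade 3 unsolicited events. The objectives and the SAP say serious, so it reads as a slip to be reconciled and does not fill the gap.

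**Conclusion.** The point holds in a limited form. On utilization, Protocol 3.1 and SAP 4.1 contradict the schedule, Protocol 5.5 and the unscheduled-visit rule: three scheduled collections after dose 1 and none after dose 2, with a possible few days from the diary. Ascertainment of medically attended events after dose 2 is weaker, not absent.

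On analysis, non-serious unsolicited events outside the clinical-interest list, and utilization, have no planned between-arm comparison after either dose. The primary analysis, the sample size and the solicited-reaction comparisons are unaffected. This is worth correcting because it limits what the trial can report about safety, but it does not threaten the main conclusion.

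The counts come directly from the documents. The precision figures rest on assumed event rates of 5% to 40%, equal between arms, and on 190 to 200 participants per arm.

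**What to change.** 1. **Reconcile the utilization window** across Protocol 3.1, SAP 4.1, the schedule of events, Protocol 5.5 and the Unscheduled Visits text. Either:
   - add utilization to the existing Visit 7 and Visit 9 calls, with a window of 42 days after each dose. The cost is the question on two calls plus the record confirmation that Protocol 5.5 requires for each reported visit; or
   - limit the utilization statement in Protocol 3.1 and SAP 4.1 to dose 1 and report that limit. The cost is a text change. If dose 2 follow-up is already complete, only this option remains.
2. **Add one descriptive table to SAP section 8**, in the ITT Population, by arm and separately after each dose: participants with at least one unsolicited adverse event of any grade, of Grade 3, related, and medically attended (the last only where utilization was collected). Give the arm difference with a 95% confidence interval, as for Secondary Objective 3. If it is added after unblinded data have been seen, label it so.
3. **Extend MedDRA coding** to all unsolicited events. For items 2 and 3 the cost is coding of terms already recorded and one table, with no added visits or participants.
4. **Align the wording** of Protocol 7.1.4 (severe) with the objectives and the SAP (serious).

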#### 3.2 Laboratory Studies

##### 3.2.1 Influenza Hemagglutination Inhibition Assay

Participants will have blood draws on Day 1 (before vaccination) and Day 28 to be stored for serum hemagglutination inhibition (HAI) antibody titers. If funding is available, HAI antibody titers will be compared between groups receiving alIV4 or IIV4-HD for each of the four influenza vaccine strains contained in the respective vaccines for that season.

### 4 STUDY ENROLLMENT AND WITHDRAWAL

#### 4.1 Subject Inclusion Criteria

Subjects who meet all of the following criteria will be eligible to participate in this interventional study.

1. Male or female age  $\geq$  65 years
2. Intention of receiving IIV and RZV based on ACIP-CDC guidelines
3. Able to speak English
4. Willing to provide written informed consent
5. Living in the community
6. Intention of being available for entire study period and complete all relevant study procedures, including follow-up phone calls and clinic visits.
7. If HIV positive, HIV should be clinically stable.

#### **4.2 Subject Exclusion Criteria**

Subjects who meet any of the following criteria will not be eligible to participate in this study:

1. IIV or recombinant influenza vaccine (RIV) receipt during the respective 2021-2022 or 2022-2023 influenza season prior to study enrollment
2. Prior receipt of recombinant zoster vaccine (Shingrix)
3. For non-COVID-19 Vaccines:
  - Receipt of any inactivated vaccine within 2 weeks prior to enrollment in this study
  - Receipt of any live vaccine within 4 weeks prior to enrollment in this study
  - Planning receipt of any non-COVID-19 vaccine during the entire period
4. For COVID-19 Vaccines:
  - Receipt of COVID-19 vaccine within 2 weeks prior to enrollment in this study. For those who have initiated a COVID-19 vaccine series, enrollment is not allowed until 2 weeks after the final dose of a COVID-19 vaccine is completed.
  - Planning receipt of a COVID-19 vaccine within 2 weeks after administration of study influenza and first dose recombinant zoster study vaccines.
5. Have acute illness or exacerbation of chronic illness within 72 hours of study vaccination
6. Hospitalization within the last 30 days for any reason
7. History of febrile illness ( $> 100.0^{\circ}\text{F}$  or  $37.8^{\circ}\text{C}$ ) within the past 24 hours prior to IIV administration
8. Has immunosuppression as a result of an underlying illness or treatment, or use of chemotherapy or radiation therapy within the preceding 12 months
9. Has an active neoplastic disease (excluding non-melanoma skin cancer or prostate cancer that is stable in the absence of therapy) \*Participants with a history of malignancy may be included if, after previous treatment by surgical excision, chemotherapy or radiation therapy, the participant has been observed for a period that in the investigator's estimation provides a reasonable assurance of sustained cure
10. A history of autoimmune disease, that requires immunosuppressive agents or any other chronic medical condition considered clinically significant by the investigator
11. Use of chronic oral or intravenous administration ( $\geq 14$  days) of immunosuppressive doses of steroids, i.e., prednisone  $> 10$  mg per day, immunosuppressants or other immune-modifying drugs within 30 days of starting this study. (Use of topical, nasal, or inhaled steroids is permitted)
12. Thrombocytopenia, bleeding disorder, or anticoagulant use contraindicating intramuscular injection (a daily aspirin may be acceptable)
13. Contraindication to IIV receipt including history of severe allergic reaction after a previous dose of any influenza vaccine; or to a vaccine component, including egg protein

14. Contraindication to RZV including history of a severe allergic reaction to any component of the RZV vaccine (including saponin or polysorbate 80) or to dose 2 of RZV
15. History of Guillain-Barré syndrome
16. History of Hepatitis C or active Hepatitis B
17. Receipt of blood or blood-derived products (including immunoglobulin) within 6 months prior to study vaccination
18. Dementia, any cognitive condition, or substance abuse that could interfere with study compliance
19. Anyone who is already enrolled or plans to enroll in another clinical trial with an investigational product within 28 days of vaccine receipt. Co-enrollment in observational or behavioral intervention studies are allowed at any time while enrollment in a clinical trial involving an investigational product (other than vaccine) may occur after 28 days following vaccine receipt
20. Any condition which, in the opinion of the investigators, may pose a health risk to the subject or interfere with the evaluation of the study objectives
21. Anyone who is a relative of any research study personnel
22. Anyone who is an employee of any research study personnel

#### **4.3 Recruitment**

Participants ≥65 years of age will be recruited from several sources at Duke University Medical Center (DUMC) and Johns Hopkins University using varying techniques. Study investigators will enroll at least 220 persons at Duke over two seasons (~110 participants per season) and ~180 persons at Johns Hopkins over two seasons (~90 per season).

The general techniques for how subjects will be recruited include the following: Study staff, including PIs and study nurses, will approach their patients in clinic directly about the study during clinic visits; notify other health care professionals in their health system about the study via letters and flyers for potential referrals; notify potential subjects about the study via study registries and recruitment service programs; letters and talks to senior groups in various venues including Senior Centers and Continuing Care Retirement Communities; advertising in newspapers; flyers posted at senior locations; letters and talks to potential referral sources; and letter campaigns to older adults in the surrounding catchment area. More specific mechanisms to DUMC and JHU are described below.

At DUMC potential subjects will be approached via the following mechanisms: 1) Elderly participants of previous vaccine studies who have agreed to enroll in future studies; 2) Duke Center for Aging Human Subjects Registry, a unique long-standing registry of over 3000 individuals who volunteer for human studies; 3) Advertising in senior citizen newspapers and general newspapers in the Durham, Chapel Hill and Raleigh areas; 4) Letter campaign to households of older adults; 5) Duke Geriatric Evaluation and Treatment Clinic (GET Clinic) and Duke University Health System primary care clinics; 6) Triangle continuing care retirement communities; 7) Duke's "Aging" network of senior centers; senior activities; and referrals from professionals who work with seniors cultivated via the work of the Center for Aging. These sources are likely to be sufficient, but if not, we will utilize other past successful strategies. An additional strategy will be the ability to send targeted notifications to potential participants through MaestroCare for Research tools. This has worked well on recent clinical trials.

At JHU subjects will be approached through 1) Johns Hopkins Frailty Registry, which as of January 2020 had over 1000 older adults enrolled; 2) Physiologic and Molecular Basis of the Syndrome of Frailty study, which contains 405 unique participants all over the age of 65; 3) COVID-19 vaccine trials, which enrolled several hundred healthy elderly individuals in 2020; 4) Database of prior volunteers at the Center for Immunization Research (CIR). If these are not sufficient, the CIR currently employs a variety of methods to recruit study participants for both outpatient and inpatient trials. Current recruitment materials include the CIR and recruitment campaign logos, volunteerism-based photos and the Center's recruitment slogan, "**Bringing Immunity to Every Community**" to build brand recognition and bring awareness to upcoming studies at the Center. Flyers and IRB-approved recruitment scripts are posted to social media (CIR Facebook, Twitter, Instagram) and websites that cater to people who are interested in study participation. For community outreach, we partner with local broadcast, cable television, and OTT (over-the-top) providers to run 15- and 30-second commercials that are IRB-approved under our general screening protocol.

At all sites, potential participants may be approached by phone call, email or text. The study will be reviewed with the participant, and if they are interested, then initial eligibility screening will take place on the phone following an IRB-approved script. A waiver of documentation of consent will be approved from the reviewing IRB in order to carry out these screening activities.

